5.3.2.1 Handling/Processing of Samples

The blood samples for adalimumab and AAA will be handled/processed as outlined below.

5.3.2.1.1 Serum Adalimumab Concentration and AAA Analysis

The blood samples for adalimumab and AAA will be centrifuged within 30-60 minutes of collection using a centrifuge to separate the serum and should be documented in the source document. Serum samples will be split into four aliquots, all being shipped to the central laboratory. Split-2 aliquots should not be shipped with the split-1 aliquots from the same draw. The serum samples will be transferred using plastic pipettes into screw capped polypropylene tubes provided by AbbVie and labeled with the drug name, type of sample (serum [SRM]), the protocol number, the subject number, the planned study day, and the assay type (PK Split 1, PK Split 2, AAA Split 1, AAA Split 2). Serum samples will be frozen within 2 hours after collection and will remain frozen at -20°C or colder until shipped and should be documented in the source document. Sites that do not have

access to a –20°C or colder freezer will need to ship the samples the day they are collected.

Additional detailed instructions for the handling and processing of samples will be provided from the central laboratory.

5.3.2.2 Disposition of Samples

The frozen blood samples will be packed in dry ice sufficient to last 3 days during transport and shipped from the study site to central laboratory according to instructions from the central laboratory manual. An inventory of the samples included will accompany the package. The central laboratory will then ship the samples to AbbVie for analysis.

5.3.2.3 Measurement Methods

Serum concentrations of adalimumab and AAA will be determined using validated ligand binding methods under the supervision of the Drug Analysis Department at AbbVie. Any additional analytes may be analyzed using non-validated methods. The residual serum volume of the samples may be used for future exploratory assay development and validation.

5.3.3 Efficacy Variables

5.3.3.1 Primary Variable

The proportion of subjects in MDA at Week 16 on adalimumab 40 mg eow plus MTX 15 mg ew as compared with subjects on MTX alone escalated to 20- 25 mg or highest tolerable dose ew.

Minimal Disease Activity (MDA)

MDA in PsA is defined as fulfilling at least 5 of the 7 following criteria:^{57,58}

- TJC \leq 1 (out of TJC68 assessed in this study)

- SJC ≤ 1 (out of SJC66 assessed in this study)
- PASI ≤ 1 or BSA ≤ 3
- Patient's assessment of pain VAS ≤ 15
- Patient's global assessment of disease activity (PtGA) VAS ≤ 20
- HAQ-DI score ≤ 0.5
- Tender enthesal points ≤ 1 (out of 8 assessed in this study)

5.3.3.2 Secondary Variables

- The following outcomes after 16 Weeks of treatment with adalimumab 40 mg eow plus MTX 15 mg ew compared with MTX alone escalated to 20-25 mg or highest tolerable dose ew:
 - Change in PASDAS from baseline
 - Change in DAPSA score from baseline
 - Change in PsAID score from baseline
 - Proportion of subjects achieving ACR 20/50/70 response
 - Change in DAS28-CRP score from baseline
 - Proportion of subjects achieving PASI 75/90/100 response among subjects with BSA $\geq 3\%$
 - Change in HAQ-DI score from baseline
 - Changes in total SF-36 score, PCS and MCS from baseline
 - Change in DLQI score from baseline
 - Change in Leeds Enthesitis Index (LEI) from baseline
 - Change in tender dactylitic digit count from baseline
- The proportion of subjects in MDA at Week 32 on each of the four different treatment regimens (Arms 1-4) in Part 2 of the study.

Psoriatic Arthritis Disease Activity Score (PASDAS)

PASDAS is a weighted disease activity measure developed specifically for PsA. It includes PhGA, PtGA, SF-36 PCS, SJC, TJC, Leeds enthesitis count, tender dactylitic count and CRP.

PASDAS score is calculated by the following equation:⁵⁹

$$\begin{aligned} \text{PASDAS} = & ((0.18 \sqrt{\text{Physician global VAS}}) \\ & + (0.159 \sqrt{\text{Patient global VAS}}) \\ & - (0.253 \times \sqrt{\text{SF36-PCS}}) \\ & + (0.101 \times \text{LN}(\text{Swollen joint count} + 1)) \\ & + (0.048 \times \text{LN}(\text{Tender joint count} + 1)) \\ & + (0.23 \times \text{LN}(\text{Leeds Enthesitis Count} + 1)) \\ & + (0.37 \text{LN}(\text{tender dactylitis count} + 1)) \\ & + (0.102 \times \text{LN}(\text{CRP} + 1)) + 2) * 1.5 \end{aligned}$$

Disease Activity in Psoriatic Arthritis (DAPSA)

DAPSA is a PsA disease activity measure, calculated by summing SJC66 + TJC68 + Patient's assessment of pain + PtGA + CRP.⁶⁰⁻⁶²

American College of Rheumatology Criteria (ACR)

The ACR is a standard criteria originally developed to measure the effectiveness of various arthritis medications or treatments in clinical trials for RA, but is also widely used in PsA. The ACR measures improvement in TJC or SJC, and improvement in at least 3 of the following 5 parameters: Patient's assessment of pain, PtGA, PhGA, physical function (HAQ-DI) and acute phase reactant (CRP). ACR 20/50/70 response is achieved if $\geq 20\%$ / $\geq 50\%$ / $\geq 70\%$ improvement in TJC or SJC as well as a $\geq 20\%$ / $\geq 50\%$ / $\geq 70\%$ improvement in ≥ 3 of the other 5 parameters.⁶³

Due to the specific of PsA (skin activity included in PtGA), ACR responses will be calculated both using PtGA and Patient's global assessment of arthritis in this study.

Disease Activity Score-28 (DAS28)

DAS28 is a weighted measure of disease activity originally developed for RA, but is also used in PsA clinical trials. DAS-28 includes TJC, SJC, PtGA and acute phase reactant (CRP in this study) and is calculated by the following equation.^{64,65}

$$\text{DAS28-CRP} = 0.56 \times \sqrt{\text{TJ}} + 0.28 \times \sqrt{\text{SJ}} + 0.36 \times \ln(\text{CRP}^* + 1) + 0.014 \times \text{PtGA} + 0.96$$

* CRP unit in the DAS28-CRP equation is expressed as mg/L.

Due to the specific of PsA (skin activity included in PtGA), DAS28-CRP will be calculated both using PtGA and Patient's global assessment of arthritis in this study.

Psoriasis Area and Severity Index (PASI) 75/90/100

PASI 75/90/100 denotes $\geq 75\%$ / $\geq 90\%$ / 100% improvement in PASI score.^{43,44}

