Table 1. Clinical Laboratory Tests

Hematology	Clinical Chemistry	Urinalysis	Other Laboratory Tests
Hematocrit	Blood Urea Nitrogen (BUN)	Specific gravity	Serum pregnancy test
Hemoglobin	Creatinine	Ketones	Urine pregnancy test
Red Blood Cell (RBC) count	Total bilirubin	pH	HIV, if applicable (testing to be conducted at local lab)
White Blood Cell (WBC) count	Albumin	Protein	HBsAg
Neutrophils	Aspartate aminotransferase (AST)	Glucose	HBsAb
Bands	Alanine aminotransferase (ALT)	Blood	HBcAb
Lymphocytes	Alkaline phosphatase	Leukocytes	HBV PCR
Monocytes	Sodium	Nitrites	HCV PCR
Basophils	Potassium		PPD or the QuantiFERON-TB Gold test
Eosinophils	Chloride		hs-CRP
Platelet count (estimate not acceptable)	Calcium		FSH*
	Inorganic phosphorus		
	Uric acid		
	Cholesterol		
	Total protein		
	Glucose		
	Triglycerides		
	Sodium bicarbonate		

* If applicable.

Assessment of Peripheral Joints

Tender Joint Count (TJC) and Swollen Joint Count

(SJC)

TJC68 and SJC66, including the DIP joints of the hands and excluding hips for swelling, will be performed as recommended for clinical trials in PsA.⁴¹ Additionally, the TJC28 and SJC28 required for the calculation of DAS28 will be extracted from the corresponding TJC68 and SJC66, respectively. The TJC/SJC assessments will be performed at the visits specified in [Appendix C](#).

Tender Joint Count (TJC)

An assessment of 68 joints (TJC68; [Appendix E](#)) will be done for tenderness by pressure manipulation on physical examination. Joint pain/tenderness will be classified as either present ("1"), absent ("0"), replaced ("9") or no assessment ("NA").

Swollen Joint Count (SJC)

An assessment of 66 joints (SJC66; [Appendix E](#)) will be done by physical examination. The joints to be examined for swelling are the same as those examined for tenderness, except the hip joints excluded. Joint swelling will be classified as present ("1"), absent ("0"), replaced ("9") or no assessment ("NA").

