5.6.2 Appropriateness of Measurements

All effectiveness measurements in this study are standard and validated.⁴¹ All clinical and laboratory procedures in this study are standard and generally accepted.

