4.3.2 Secondary Efficacy Endpoints

The secondary efficacy endpoints include:

- At Week 16:
 - Change from baseline in PASDAS
 - Change from baseline in DAPSA score
 - Change from baseline in PsAID score
 - Proportion of subjects achieving ACR 20/50/70 response
 - Change from baseline in DAS28-CRP score

- Proportion of subjects achieving PASI 75/90/100 response (for subjects with BSA \geq 3% at baseline)
- Change from baseline in HAQ-DI score
- Changes from baseline in SF-36PCS and SF-36MCS
- Change from baseline in DLQI score
- Change from baseline in Leeds Enthesitis Index (LEI) (for subjects with presence of enthesitis at baseline)
- Change from baseline in tender dactylitic digit count (for subjects with presence of dactylitis at baseline)
- The proportion of subjects in MDA at Week 32.

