6.3 Secondary Efficacy Analyses

Part 1 Analysis

A complete list of secondary efficacy endpoints is provided in Section 4.3.2. Binary endpoints will be analyzed in a similar way as the primary endpoint.

For the continuous endpoints, the change from baseline at Week 16 will be analyzed using MMRM with treatment, the stratification factor of duration of prior MTX use (≤ 3 months or > 3 months), visit, and treatment-by-visit interaction as fixed effects, subject as random effect and baseline measurement as a covariate. The MMRM analysis is based on observed data. The LS mean, 95% CI and standard error for each randomized treatment group, the LS mean of the treatment difference and its associated 95% CI and p-value from the MMRM model will be presented.

Long Term Analysis

The achievement of MDA at Week 32 on each of the four different treatment regimens will be evaluated. The proportion of subjects who achieved MDA at Week 32 will be summarized by counts and percentages for the four treatment regimens. Point estimate and 95% CI using normal approximation will be provided for each treatment regimen as well. The subjects who were rescued prior to Week 32 will be considered as non-

responders (MDA = 0) at Week 32. No comparison between treatment regimens will be performed.

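### As written, ACR 20/50/70 response needs threshold improvement in only one of the two joint counts, so a subject whose other count falls short or worsens can still be a responder

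*Protocol*

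**What the plan says.** The only definition of ACR response is in Protocol 5.3.3.2. The descriptive sentence reads: "The ACR measures improvement in TJC or SJC, and improvement in at least 3 of the following 5 parameters". The sentence that sets the 20, 50 and 70% thresholds uses the same connective: "improvement in TJC or SJC as well as a" matching improvement in at least three of the five other parameters. Those five are patient-assessed pain, PtGA, PhGA, HAQ-DI and CRP. Neither joint count is among them. The same section has each response calculated with two different patient globals.

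The SAP adds no algorithm. Section 4.1 lists the measure among the secondary objectives, and section 4.3.2 lists the endpoint as "Proportion of subjects achieving ACR 20/50/70 response". Section 6.3 then says: "Binary endpoints will be analyzed in a similar way as the primary endpoint". That means a stratified CMH test with non-responder imputation at the two-sided 0.05 level. Section 6.4 carries the same endpoints into the by-visit summaries and the Week 32 summaries by regimen.

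**The concern.** A programmer who follows the plan exactly would pass the joint component on tender joints alone or on swollen joints alone. No clause limits what the other count does. It may improve but miss the threshold, stay flat, or get worse, bounded only by the 68 joints assessed for tenderness and the 66 assessed for swelling.

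Elsewhere the protocol keeps both counts in play. Inclusion criterion 4 requires at least three tender and at least three swollen joints. PASDAS, DAPSA and DAS28-CRP each include both counts, so worsening in either raises the score. ACR response is the measure in which one count can be ignored entirely.

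At stake is the meaning of the Week 16 ACR 20, 50 and 70 endpoints. With two patient globals these become 3 × 2 = 6 response variables. The by-visit and Week 32 versions inherit the same rule. The entry floor makes the joint component easy to meet: a subject entering with three swollen joints who loses one has improved by 1/3 = 33% and passes at the 20% level, whatever the tender count does.

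**Working it through.** **The plan's own figures.** The documents give no ACR response rate and no ACR component rate. Their one design figure is the power for MDA, 40% against 20%, two-sided 0.05. With pooled variance under the null, power is Φ[(0.20 − 1.96·√(2·0.3·0.7/n)) / √((0.4·0.6 + 0.2·0.8)/n)]. This gives 92.7% at n = 120 per arm and 89.9% at n = 108 (120 less 10%), so the stated 90% is reproduced to rounding. The ACR definition does not enter this calculation.

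**The rule applied to example subjects.** These subjects are invented to test the logic. Improvement is (baseline − Week 16)/baseline. In each case three of the five other items are taken to have improved by 70%.

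- TJC 20 to 6: (20 − 6)/20 = 70% better. SJC 10 to 66: (66 − 10)/10 = 560% worse. Under the written rule this is a responder at 20, 50 and 70. If both counts were required, it is a non-responder at all three.
- TJC 20 to 68 (48/20 = 240% worse), SJC 10 to 3 (70% better). The result is the same with the counts reversed.
- TJC 20 to 6 (70% better), SJC 10 to 4 (60% better). Under the written rule this is an ACR70 responder. If both were required, it is an ACR50 responder but not an ACR70 responder. Nothing has worsened here; the other count simply misses the threshold.

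**Direction.** Anyone who reaches the threshold on both counts also reaches it on at least one. Every responder under a both-count rule is therefore a responder under the written rule, and the written rule can only give an equal or higher rate in each arm.

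**Illustration for the joint component only.** Assume a share p of subjects reaches the threshold on each count, with an underlying bivariate normal correlation ρ. Then P(both) = Φ₂(z, z; ρ) with z = Φ⁻¹(p), and P(either) = 2p − P(both). For p = 0.40, P(both) is 0.206, 0.239 and 0.278 at ρ = 0.3, 0.5 and 0.7. P(either) is then 0.80 minus these: 0.594, 0.561 and 0.522.

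| Assumed p on each count | Either count, ρ 0.3 to 0.7 | Both counts, ρ 0.3 to 0.7 |
|---|---|---|
| 20% | 33 to 29% | 7 to 11% |
| 40% | 59 to 52% | 21 to 28% |
| 50% | 70 to 63% | 30 to 37% |
| 60% | 79 to 72% | 41 to 48% |

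The gap between the columns is the share reaching the threshold on exactly one count. At p = 40% it is 0.594 − 0.206 = 0.388 down to 0.522 − 0.278 = 0.244. It mixes subjects whose other count improved too little with those whose other count worsened. The documents give nothing with which to split it.

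**The case against.** The strongest reply is that the table overstates what matters. It covers one component. A responder must also pass three of five other items at the same threshold, so the effect on the ACR rate could be much smaller. The values of p and ρ are assumed. The comparison is with both counts at threshold, so most of the gap could be subjects whose other count improved but not enough. All of this stands, and the table should be read only as an illustration.

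It can also be said that the plan tolerates a failing joint count elsewhere. MDA needs five of seven criteria, so a subject can be in MDA with TJC or SJC above its limit. That is true, but the miss then uses up one of the two allowed. Under the ACR rule the failing count costs nothing. DAPSA, PASDAS and DAS28-CRP would still register worsening in either count, which limits the damage to the overall picture but does not repair the ACR endpoints.

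Several stronger readings are tempting but unsupported:

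- That tender joints can carry the whole endpoint. They can carry only the joint component, and the rule is symmetric, so swollen joints can do the same.
- That open-label assessment turns this into bias favouring adalimumab. Protocol 5.3.1.1 asks for an independent joint assessor where possible and the same assessor at each visit. It does not say the assessor is blinded, so the mitigation is partial, but no direction of bias follows from the text.
- That the rule contradicts Protocol 5.6.2, "All effectiveness measurements in this study are standard and validated". That conflict could be shown only from the source cited for the criteria, which is not part of the documents. The point here rests on the logic of the stated rule alone.

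**Conclusion.** The point holds as a defect in a stated rule, not as missing detail. Followed literally, the plan counts as ACR responders subjects who reach the threshold on one joint count only, including any whose other count worsens, provided three of the five other items pass. Relative to a both-count rule this can only raise ACR 20/50/70 rates, in both arms, at Week 16, by visit and at Week 32.

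Its size on the ACR endpoints cannot be computed from the documents. On the joint component alone, with 40% assumed on each count and correlation 0.3 to 0.7, 52 to 59% pass as written against 21 to 28% if both were required.

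A reader might infer that the treatment comparison is biased. The documents do not show this: rates rise in both arms, and the change in their difference cannot be derived. Nor is the primary conclusion touched, because neither MDA nor the sample size uses the ACR definition.

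**What to change.** In both sentences of the ACR definition in Protocol 5.3.3.2, require the threshold improvement in both TJC and SJC. State the same definition in SAP 4.3.2 before database lock, so that the programmed endpoint matches at Week 16, by visit and at Week 32. If the either-count rule is what the sponsor intends, it should be stated as deliberate and justified in the same two places.

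The change is a few words in the protocol and one line in the SAP, with no new data collection and no effect on sample size. The downside is lower reported ACR response rates in both arms.

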5.3.3.3 Exploratory Variables

Clinical Effectiveness Variables

Clinical effectiveness outcomes listed under the secondary variables at Week 32 on the 4 different treatment regimens (Arms 1-4) in Part 2 of the study.

Ultrasound Variables

- The change in Global OMERACT-EULAR synovitis score (GLOESS) from baseline to Week 16 in subjects who had adalimumab introduced in combination with MTX compared with those who had MTX escalated to 20-25 mg ew or highest tolerable dose.
- The change in OMERACT enthesitis score from baseline to Week 16 in subjects who had adalimumab introduced in combination with MTX compared with those who had MTX escalated to 20-25 mg ew or highest tolerable dose.
- The change in Global OMERACT-EULAR synovitis score (GLOESS) from Week 16-32 in the 4 arms of Part 2 of the study.

- The change in OMERACT enthesitis score from Week 16-32 in the 4 arms of Part 2 of the study.

5.3.4 Safety Variables

Screening assessments will include medical history, vital signs, physical examination, and clinical laboratory tests. The following safety evaluations will be performed during the study: concomitant medication review, adverse event (AE) monitoring, vital signs, physical examination (if required) and laboratory tests.

5.3.5 Pharmacokinetic and Immunogenicity Variables

For subjects receiving adalimumab, blood samples will be collected for determination of adalimumab serum concentrations and the presence of anti-ADA antibodies (AAA) as specified in [Appendix C](#).

5.3.6 Exploratory Research Variables and Validation Studies

Optional samples may be collected to conduct exploratory investigations into known and novel biomarkers. The types of biomarkers to be analyzed may include, but are not limited to: nucleic acids, proteins, lipids or metabolites.

Biomarker assessments may be used to assess and generate prognostic, predictive, pharmacodynamic, or surrogate biomarker signatures. These assessments may be explored in the context of PsA or related conditions and/or adalimumab or drugs of similar classes. The results from these analyses are exploratory in nature and may not be included with the study report.

The samples may also be used to develop new therapies, research methods or technologies. In addition, samples from this study may be banked for future use. Samples may then be used to validate putative biomarker signatures obtained from a prospective study, leading to the development of diagnostic tests.

5.4 Removal of Subjects from Therapy or Assessment

5.4.1 Discontinuation of Individual Subjects

A subject may withdraw from the study at any time. The Investigator may discontinue any subject's participation for any reason, including an adverse event, safety concerns or failure to comply with the protocol.

Subjects will be withdrawn from the study if any of the following occur:

- Clinically significant abnormal laboratory result(s) or adverse event(s), as determined by the Investigator in consultation with the AbbVie TA MD.
- The Investigator believes it is in the best interest of the subject.
- The subject requests withdrawal from the study.
- Inclusion and exclusion criteria violation was noted after the subject started study drug, when continuation of the study drug would place the subject at risk as determined by the AbbVie TA MD.
- Introduction of prohibited medications or dosages when continuation of the study drug would place the subject at risk as determined by the AbbVie TA MD.
- Joint surgery
- The subject becomes pregnant while on study medication.
- Subject has known dysplasia of the gastrointestinal tract or malignancy, except for localized non-melanoma skin cancer. Discontinuation for carcinoma in-situ of the cervix is at the discretion of the Investigator.
- Subject is diagnosed with lupus like syndrome, multiple sclerosis or demyelinating disease.
- Subject is non-compliant with TB prophylaxis.
- The subject develops tuberculosis, or any other significant or opportunistic infections.
- Subject is significantly non-compliant with study procedures which would put the subject at risk for continued participation in the trial in consultation with the AbbVie TA MD.

If, during the course of study drug administration, the subject prematurely discontinues study drug use, the procedures outlined for the PD visit must be completed within 2 weeks of the last dose of study drug, and preferably prior to the initiation of another therapy. However, these procedures should not interfere with the initiation of any new treatments or therapeutic modalities that the Investigator feels are necessary to treat the subject's condition. Following discontinuation of the study drug, the subject will be treated in accordance with the Investigator's best clinical judgment.

A final phone call will be made to the subject approximately 70 days (\pm 7 day window) after the last dose of study drug to determine the status of any ongoing AEs/SAEs or the occurrence of any new AEs/SAEs (as described in Section 5.1.2.2). The information will be recorded on the appropriate eCRF page.

All attempts must be made to determine the date of the last study drug dose and the primary reason for premature discontinuation. The information will be recorded on the appropriate eCRF page.

For subjects who are considered lost to follow-up, reasonable attempts must be made to obtain information on the final status of the subject. At a minimum, two phone calls must be made and one certified letter must be sent and documented in the subject's source documentation.

Subjects who discontinue the study prematurely will not be replaced.

